U-	Unpredictable
U-Threat	Uncertain Threat

1.0 PROJECT SUMMARY/ABSTRACT

Alcohol use disorder (AUD) affects millions and is one of the leading causes of preventable death worldwide. In the US, pharmacotherapy for AUD is under-utilized; related to the fact that there are only three FDA-approved drugs to treat patients with AUD. These medications work well for some but have small to moderate effect sizes on drinking outcomes. The development of more efficacious pharmacotherapies for AUD is a top public health priority. A recent emphasis in psychiatric medication development is the use of reliable human laboratory measures of AUD dysfunction to test promising compounds to directly inform and power large-scale mechanistic clinical trials. PI [name] and Co-I [name] have developed an assay of stress reactivity that is robustly related to drinking behavior and AUD. This assay reflects a negative reinforcement model of AUD and is reliably captured in the lab using complimentary objective psychophysiological (i.e., startle eyeblink potentiation) and functional neuroimaging measures. Using this model, we have uncovered that suvorexant (SUV) – a dual receptor antagonist of the orexin system, FDA-approved for insomnia – acutely modifies our AUD target in healthy adults, while sparing changes in other markers of stress reactivity. Compelling animal and human evidence together suggest that the orexin system is critically involved in stress-related alcohol use. The overarching goal of this study is to systematically advance this line of work to uncover if, how, and for whom orexin antagonism modifies brain-behavior stress targets of AUD to inform and power future large scale clinical trials. The study is a targeted double-blind, between-subjects, randomized clinical trial design with repeat lab assessment. A total of eighty subjects with AUD will complete our psychophysiological stress paradigm at baseline. They will return to the lab days later to repeat the protocol following administration of a single dose of either 10mg SUV or placebo (40 subjects/arm). Participants are then instructed to take daily 10mg capsules of SUV or placebo for the next 4-weeks before returning for a post-treatment lab assessment. Daily reports of medication adherence, side-effects, sleep, alcohol use, and mood will be collected via smartphones.

This multimodal design allows for a well-controlled test of whether an acute dose of SUV (Aim 1) and/or daily use of SUV (Aim 2) modifies brain-behavior targets of AUD dysfunction, particularly within individuals with high objective baseline stress reactivity. We will also examine whether daily SUV changes alcohol behavior, and whether this change in behavior is linked to brain-behavior change (Aim 3). Findings from this study will provide critical new knowledge regarding if and how orexin antagonism can be leveraged to treat AUD. The findings will also be used to inform and power a large-scale mechanistic clinical trial of SUV for AUD.

2.0 BACKGROUND/SCIENTIFIC RATIONALE

Alcohol use disorder (AUD) is a serious public health issue and a leading cause of preventable death worldwide¹. In the US, there is a paucity of pharmacotherapies for AUD, related to the fact that there are only three FDA approved drugs used to treat patients²⁻³. These medications work well for some but have small to moderate effect sizes with ~50-60% relapsing within 12 weeks of treatment⁴⁻⁵. The development of more efficacious pharmacotherapies for AUD is urgently needed and a top public health priority⁶⁻⁷; though ushering compounds through the clinical testing process and into the AUD clinic has been a well-documented challenge.

A recent emphasis in medication development is the use of valid and reliable human laboratory measures of AUD pathophysiology to test promising compounds to inform and power targeted clinical trials⁷⁻⁹. The ultimate goal is to more quickly identify compounds deserving of clinical testing and accelerate the pace of mechanistic drug discovery. PI [name] and Co-I [name] have developed a reliable assay of stress reactivity that is robustly associated with drinking behavior and AUD¹⁰. We have shown that greater brain (i.e., anterior insula [aINS] and dorsal anterior cingulate cortex [dACC]) and behavioral (i.e., startle eyeblink) reactivity to threats that are uncertain (U-threat) is associated with greater frequency of drinking, changes in drinking over time, and onset of AUD¹¹. Individuals with AUD reliably exhibit greater brain-behavior reactivity to U-threat compared with controls, and magnitude of reactivity correlates with AUD severity¹¹⁻¹⁴. These findings have been replicated by other labs and coincide with studies showing alcohol intoxication selectively and effectively dampens reactivity to U-threat (but not predictable threat; P-threat)¹⁵⁻¹⁸. We have therefore developed a negative reinforcement model of AUD that is reliably captured in the lab using objective, complimentary psychophysiological and neuroimaging measures. This paradigm is now being incorporated into several 'Fast-Fail' proof-of-concept medication trials.

Novel preclinical research indicates that the hypocretin/orexin (ORX) hypothalamic neuropeptide system plays a pivotal role in alcohol abuse. In rodents, antagonism of ORX receptors prevents alcohol-seeking behavior and binge-like alcohol drinking, while preserving motivation for natural rewards¹⁹⁻²². ORX receptor antagonism also robustly reduces behavioral and psychophysiological stress reactivity to threat and pharmacological challenge²³⁻²⁴. ORX antagonism may therefore be an effective strategy for disrupting the negative reinforcement cycle of addiction. Remarkably, using a within-subjects, placebo-controlled design our prelim data indicates an acute dose of suvorexant (SUV) – an FDA-approved dual ORX receptor antagonist for insomnia – robustly reduces behavioral reactivity to U-threat in adults, while sparing changes in other psychophysiological markers of threat sensitivity less relevant to AUD. ORX antagonism selectively engages the U-threat target, providing compelling evidence it is a promising pharmacological treatment for individuals with AUD and high U-threat reactivity, who frequently engage in stress-related alcohol use^{22, 25-28}.

No prior study has measured stress-related ORX target engagement in humans to uncover how ORX antagonism can be leveraged to treat AUD. The overarching goal of the current study is to advance ORX translation to the AUD clinic using a proof-of-concept

double-blind, between-subjects, randomized clinical trial design with repeat lab assessment.

All subjects will complete three lab visits of psychophysiological data collection. A subset of 20 subjects per arm (40 total) will also complete our stress task during simultaneous startle and functional magnetic resonance imaging (fMRI), pre- and posttreatment. This design allows us to address if, how, and for whom ORX antagonism modifies brain-behavior stress targets to inform and power future large scale mechanistic clinical trials.

3.0 Objectives/Aims

Aim 1. Does an acute dose of suvorexant decrease reactivity to U-threat? H1: Relative to placebo, SUV will acutely dampen psychophysiological reactivity to U-threat, but not P-threat.

Aim 2. Does daily use of suvorexant decrease reactivity to U-threat? H2a: 4-weeks of SUV will result in greater reductions in psychophysiological reactivity to U-threat compared with placebo, and these changes will be specific to U-threat. **H2b:** SUV-related change in U-threat reactivity will be greatest amongst those with higher baseline U-threat reactivity. Exploratory: Daily SUV will similarly result in decreases in aINS and dACC reactivity and connectivity during U-threat relative to placebo, and brain change will correlate with startle change.

Aim 3. Does daily use of suvorexant change alcohol behavior, and is this change linked to brain-behavior U-threat change? H3a: Daily SUV will result in greater reductions in proportion of heavy drinking days (PHDD) and drinks per drinking day (DPDD). **H3b:** SUV-related changes in PHDD and DPDD will be greatest in those with higher U-threat reactivity. **H3c:** In all subjects, changes in alcohol behavior will correlate with changes in brain-behavioral U-threat reactivity.

Study duration. Participants will complete a Screening Session and three to five in-person laboratory sessions (dependent upon randomization) over the course of 1.5 – 2 months.

4.0 Eligibility

4.1 Inclusion Criteria

Adults 18-65 years old will be enrolled in this study. Participants will be required to be generally medically and neurologically healthy. They will also be required to meet current DSM-5 diagnosis of moderate to severe AUD and engage in heavy alcohol use defined as drinking ≥ 14 standard drinks per week if male, and ≥ 7 standard drinks per week if female.

4.2 Exclusion Criteria

Exclusion criteria for all subjects will be: (a) clinically significant medical or neurologic condition or neurocognitive dysfunction that would affect function, and/or task performance, and/or interfere with the study protocol, and/or be contraindicated for suvorexant (SUV), including narcolepsy, complex sleep behaviors, severe hepatic impairment, and compromised respiratory function such as COPD, and severe obstructive sleep apnea; (b) current or past major DSM-5 psychiatric disorder including mania, schizophrenia, psychosis, suicidality (as defined by a score of 5 or higher on the Beck's Scale for Suicidal Ideation - Lifetime [SSI]), major depressive disorder (MDD), or obsessive-compulsive disorder (OCD); (c) current substance use disorder for any substance, except for mild cannabis use disorder; (d) treatment seeking for AUD due to the study design and experimental nature of SUV; (e) currently pregnant (positive pregnancy test), lactating, or not agreeing to use birth control methods during the duration of the trial (women); (f) recent (in the past 2 months) use of any psychoactive medications; (g) current antihistamines use; (h) current use of strong or moderate inhibitors of CYP3A liver enzymes; (i) current use of strong CYP3A inducers; (j) current use of digoxin; (k) night shift work; (l) smoke 5 or more cigarettes (or electronic equivalent) per day and are thus susceptible to acute nicotine withdrawal during lab visits; (m) obesity as defined by a body-mass index (BMI) greater than 35, as calculated from weight and height self-report; (n) lack of fluency in English; (o) acute alcohol withdrawal the day of the lab sessions, defined as a score >8 on the Clinical Institute Withdrawal Assessment of Alcohol Scale Revised (CIWA-Ar)²⁹; (p) unwilling/unable to sign the informed consent document; (q) under 18 years old or over 65 years old at the time of enrollment; (r) history of traumatic brain injury (as defined by The American Congress of Rehabilitation as a traumatically induced physiological disruption of brain function - i.e., the head being struck, the head striking an object, and/or the brain undergoing an acceleration/deceleration movement, such as whiplash - without direct external trauma to the head), as manifested by at least one of the following: any loss of consciousness; any loss of memory for events immediately before or after the injury; any alteration in mental status at the time of the incident; or focal neurological deficits that may or may not be transient.

Additional exclusion criteria for all participants pertaining to the fMRI scan include: a) presence of ferrous-containing metals within the body (e.g., aneurysm clips, shrapnel/retained particles) or b) inability to tolerate small, enclosed spaces without anxiety (e.g., claustrophobia).

Acute alcohol intoxication, verified via breath test, will disqualify immediate participation for lab tasks; though subjects may be able to re-schedule the visit for a later date. Upon arrival to the lab sessions, individuals will provide a urine sample for drug screen and complete a corresponding detailed Timeline Follow-back (TLFB)³⁰ of their substance use. If individuals test positive for recreational substance use and self-report use within the past 24-hours their lab visit will be re-scheduled for a later date.

4.3 Excluded or Vulnerable Populations

No individuals will be allowed to participate in the study if they are < 18 years of age or > 65 years of age. This study will exclude children (<18 years of age).

This age range was chosen to minimize the potential for adverse medication side-effects. Limiting the sample to adults younger than 65 also reduces potential heterogeneity in brain structure and function, and psychophysiological stress reactivity, which could confound data interpretation in the current sample size.

Individuals younger than age 18 will be excluded because suvorexant is not FDA-approved for use in children.

The study will also exclude individuals who are pregnant, nursing, or are trying to get pregnant to ensure safety of the fetus/child during procedures. This study will exclude prisoners.

5.0 Subject Enrollment

- We propose to recruit from multiple sources with the intent to enroll a community sample.
- Participants will be recruited via print advertisements across the central Ohio area, word-of-mouth referrals (including through the OSU emergency department (ED)), and internet and social media postings (e.g., craigslist, Facebook, Snapchat, Instagram), and through OSU websites (such as Study Search) and electronic newsletters.
- We expect to recruit up to 120 participants in 2 years.
- Advertisements will include a QR code that when scanned will direct interested individuals to the study's online Recruitment Survey on REDCap. If the individual chooses, they will complete the online survey that assesses for initial eligibility criteria.
- The study staff will determine potential participants' eligibility for the research.
- If an individual meets this initial eligibility criteria on the survey, trained clinical research staff or investigators will call the individual and complete a phone screen to further assess eligibility for the research study. Data from participants not eligible for the study based on the initial phone screen will be destroyed once they are determined to be ineligible.
- In collaboration with [name], Professor of Emergency Medicine at the OSU Wexner Medical Center, we propose to also recruit from the OSU ED. IRB approved and trained research specialists, employed by [name], who work in the OSU ED will assist in recruitment procedures by conducting the phone screen verbally in-person with interested participants.

The research specialists are a part of an established research initiative and are specifically trained to enroll individuals in the ED into IRB approved research studies. Thus, phone screening individuals in the ED is a part of the research specialists' routine job responsibilities.

- As outlined in the phone screen, the OSU ED research specialists will read a brief description of the study and if the individual is interested, the phone screen will be completed. Study staff will not access medical records at any point during the recruitment process.
- Following the completion of the phone screen, potentially eligible individuals will be scheduled for a Screening Session. Participants will be given the choice to complete the Screening Session online or in-person to accommodate potential limited access to the internet.
- During the Screening Session, participants will provide informed consent. Specifically, once the procedures are explained to them in detail, subjects will be given ample time to read the consent form, formulate questions and ponder the responses. Subjects will have time between initial contact and the scheduled testing to discuss participation with people of their choice; the initial laboratory session date will be scheduled for their convenience. We will emphasize to subjects the voluntary nature of their participation in the study. Subjects will also be told that they are free to drop out of the study at any time for any reason.
 - **Online Screening Sessions:** Consent will be collected via REDCap software. The authenticity requirements involve Remote Signing, Username & Password. During the phone screen, if participants are found to be eligible, they will establish a password with study staff. The study staff will enter the passcode in the participant's REDCap record. Participants are sent a link to sign the consent form in REDCap via email, which does not include the password. Participants are then asked for the password which is cross referenced with the password already on file in the REDCap project. The completed consent form will be downloaded and stored in the PI's laboratory in a locked cabinet and locked office. A copy of the signed consent is emailed to the participant by REDCap.
 - **In-person Screening Sessions:** Consent will be collected via REDCap software. The authenticity requirements involve in-person signing. Participants can provide ID, insurance card, name and date of birth, etc. for study staff to verify their identity. The completed consent form will be downloaded and stored in the PI's laboratory in a locked cabinet and locked office. A copy will be given to participants.
- At the Screening Session a clinically trained study staff member will perform the Structured Clinical Interview for DSM-5 (SCID-5)³¹ and administer a small battery of questionnaires. MD level physician will review his/her medical and neurological history. Initial eligibility for the research will be

documented in the research record. Final determination of subject eligibility will be made by the PI or the PI in consultation with research staff.

- Following the Screening Session, eligible participants will be randomized to a treatment group (i.e., SUV or placebo) and protocol arm (i.e., EMG/EEG only or EMG/EEG + fMRI). Treatment group randomization will be double-blinded.
- Research study staff will monitor the participants throughout the course of the research to ensure that they still meet eligibility criteria, and their continuing eligibility will be documented by the research staff. This will include ensuring abstinence from alcohol at both laboratory visits. It will also ensure that no participant is pregnant at either session.
- Upon enrollment into the study, participants will be required to agree and consent to not operating heavy machinery, including driving a vehicle, for at least 24-hours after the Acute Drug Challenge visit due to day-time drug administration.
- Participants will also be instructed that they will be required to fast for at least 2-hours prior to the Acute Drug Challenge visit to avoid interactions between food and SUV metabolism. The Acute Drug Challenge visit will therefore begin at approximately 9-10am.
- Following the Acute Drug Challenge visit, participants will be instructed to take either SUV or placebo, dependent upon their randomized treatment group, once daily before bed for 4 weeks. Participants will complete daily online clinical assessments. The PI and study staff will monitor potential side effects and drug adherence throughout the duration of the 4 weeks.
- Participants will return to the lab at the end of the 4 weeks and complete a third EMG/EEG, and second fMRI (dependent upon randomization).
- Participants will be debriefed and provided AUD treatment referrals as appropriate at the end of their study participation.

- **Termination Criteria:** Participants may be terminated for any of the following: (a) completion of study; (b) participant request to exit or withdraw consent; (c) development of suicidal or homicidal ideation requiring hospitalization; (d) development of a systemic, medical, neurologic or psychiatric illness requiring treatment that would exclude participation; (e) clinical deterioration (see below); (f) non-compliance with study protocol requirements including refusing to consent to not driving for at least 24-hours after Lab Visit 2 (Acute Drug Challenge) due to day-time drug administration; (g) significant worsening of AUD symptoms that would require treatment; and (h) a positive pregnancy test. If alcohol tests are positive, participants will be given the option to reschedule. If breath tests are again positive, participation will be terminated.

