Study Overview. The study is a double-blind, between-subjects, randomized clinical trial with a multi-session lab paradigm (see Figure 1). Participants will first complete an initial Screening Session where they will complete an assessment of study eligibility (described above), a clinical interview, and questionnaires. If participants are found to be eligible, they will be randomized to a treatment group (SUV or placebo) and protocol arm (BEHAVIOR or BRAINS Group). Those in the BEHAVIOR Group will complete electromyography (EMG)/electroencephalography (EEG) only and those in the BRAINS Group will complete EMG/EEG + fMRI.

Therefore, participants have a chance of being randomized to four different groups (20 participants/group): 1) BEHAVIOR - SUV; 2) BEHAVIOR - Placebo; 3) BRAINS - SUV; and 4) BRAINS - Placebo.

BEHAVIOR Group Overview:

Following the Screening Session, participants randomized to the BEHAVIOR group will come in-person to Lab Visit 1 where they will complete the psychophysiological stress paradigm and Alcohol Cue Reactivity EEG task. Days later, they will return to the lab for Visit 2 (Acute Drug Challenge) and repeat the protocol during their first dose of medication (placebo or 10mg SUV). Next, they will be instructed to take a 10mg dose of SUV (or placebo) each night before bed for 4-weeks. Daily online assessments of medication compliance, side-effects, alcohol use, mood, and sleep will be collected. During the final week of the protocol subjects will return for Lab Visit 3 to repeat the paradigm (dose taken night prior, as prescribed).

BRAINS Group Overview:

Following the Screening Session, participants randomized to BRAINS Group will complete the same procedures as above with the exception of completing two additional fMRI visits pre- and post-treatment. Therefore, participants will complete: Lab Visit 1 (EMG/EEG), Lab Visit 2 (fMRI), Lab Visit 3 (Acute Drug Challenge), four weeks of SUV (or placebo) administration with daily online assessments, Lab Visit 4 (EMG/EEG), and Lab Visit 5 (fMRI).

Screening. During the Screening Session, participants will complete an assessment of study eligibility, the Structured Clinical Interview for DSM-5 (SCID-5)³¹ with trained study staff, and a short battery of self-report questionnaires (see Table 1 and Table 2). Participants will be given the choice to complete the Screening Session online or in-person to accommodate potential limited access to the internet.

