13.0 Regulatory Requirements

13.1 Informed Consent

- During the initial assessment, the nature of the research project will be described to participants. A written summary, in lay terms, of the research project will be provided to the participants in the written informed consent document that the participants will review. The consent document will inform

the participants of the voluntary nature of the study procedures, the purpose of the study, the procedures to be followed, the duration of the study, the risks associated with suvorexant, the risks associated with startle and fMRI procedures such as exposure to loud noise bursts, as well as the potential benefits to the community at large. Women will agree that they are not pregnant, nursing, or planning to become pregnant. Participants will be informed that a urine sample for a pregnancy/toxicology screen and a breathalyzer will be obtained at both sessions. Written informed consent will be obtained by the PI or designated research staff and the participant will receive a copy of the signed consent form. Participants will be informed that they can discontinue participation at any time without penalty.

- Each member of the research team will complete the HIPAA and CITI human subjects trainings and will be trained in the research protocol and will have reviewed the informed consent document and assent forms themselves.
- The informed consent document will be stored in a separate locked file cabinet from any other research files in a locked office. Only research staff on this specific research study will have access to the informed consent documents.

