- Confidentiality of Drug Tests Prior to Scans or Assessment: The results of the urine drug and pregnancy screens will remain confidential. The only individuals who will have knowledge of the results of these tests are research staff directly working on the project.
- The only PHI we are collecting in this study include the participants name and contact information (phone number, email address, home address). The reasons that we are collecting this information include: the participants name for the informed consent document, phone number and email address to schedule lab appointments.

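### The general pregnancy and breath-test wording covers two unnamed sessions in a three- or five-visit design, and neither test is expressly placed before the first capsule

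*Combined protocol and SAP*

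**What the plan says.** Three general statements count sessions in pairs. Section 5.0 says of continuing-eligibility monitoring: "This will include ensuring abstinence from alcohol at both laboratory visits". It then adds: "It will also ensure that no participant is pregnant at either session". Section 13.1 tells participants that "a urine sample for a pregnancy/toxicology screen and a breathalyzer will be obtained at both sessions". None of the three names the sessions.

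Sections 3.0 and 6.0 describe a different visit count. BEHAVIOR participants attend three lab visits and BRAINS participants five. Section 5.0 itself mentions a third EMG/EEG session.

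The first dose is taken at the Acute Drug Challenge, which is Visit 2 for BEHAVIOR and Visit 3 for BRAINS. For BEHAVIOR, Section 6.0 says: "Days later, they will return to the lab for Visit 2 (Acute Drug Challenge) and repeat the protocol during their first dose of medication". Under Administration Timing, the capsule is given at the CRC when the participant arrives, and the move to the laboratory comes later. The measures listed for Time 0 are the sleepiness, anxiety, drug-effect and mood scales, oxygen saturation, heart rate and blood pressure.

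Other rules are not limited to two sessions. Section 4.2 says: "Acute alcohol intoxication, verified via breath test, will disqualify immediate participation for lab tasks", and also: "Upon arrival to the lab sessions, individuals will provide a urine sample for drug screen". The termination criteria in Section 5.0 list a positive pregnancy test. They offer rescheduling after a positive alcohol test and termination after a repeat. Section 6.0 (fMRI Data Collection) requires a urine pregnancy test before the scan. Section 8.0 lists the urine pregnancy test among the study's data sources.

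**The concern.** A rule for two sessions cannot be applied as written to three or five visits, because staff cannot tell which visits it means. The visit that matters most is the Acute Drug Challenge. Drug exposure starts there, and the rest of the capsules are handed over at its end. For BEHAVIOR participants, the next in-person visit described is in the final week of treatment.

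The protocol's own reasoning makes the order of test and capsule matter. Section 7.0 excludes pregnant women because fetal safety during exposure to suvorexant cannot be assured. It also reports advice to avoid combining alcohol with this drug class. The rules on a positive result prevent a first exposure only if the result is known before the capsule is swallowed. At stake is a pregnancy that was missed or that began after an earlier test and, to a lesser degree, dosing someone who has been drinking.

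**Working it through.** The plan gives no figure to reproduce, and the point involves no alpha, power or effect size. The check is a visit count and a comparison of the relevant text.

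**Visits against the two-session wording** (Sections 3.0, 5.0, 6.0 and 13.1)
- BEHAVIOR: 2 × 20 = 40 participants, 3 lab visits. A two-session rule read literally leaves 3 − 2 = 1 visit uncovered.
- BRAINS: 2 × 20 = 40 participants, 5 lab visits. The same reading leaves 5 − 2 = 3 visits uncovered.

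**Pregnancy tests tied to a named visit** (Section 6.0, fMRI Data Collection)
- BEHAVIOR: 0 of 3.
- BRAINS: 2 of 5, namely the two fMRI visits (Visits 2 and 5). The first of these precedes the first dose.
- At the Acute Drug Challenge itself: none in either group.

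Screening does not clearly fill the BEHAVIOR gap. It may be done online, and no urine test is described there.

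**What each rule settles about the first capsule**
- Section 4.2, pregnancy exclusion: a positive test excludes, but no visit is given.
- Section 4.2, breath rule: stated as a condition for the lab tasks. The Acute Drug Challenge includes a lab task, so the rule reasonably covers that day. Its order relative to the capsule is not stated.
- Section 4.2, urine on arrival: stated for the drug screen. Section 13.1 joins the pregnancy and toxicology screens, but within the two-session wording.
- Section 5.0, termination criteria: these give the consequences of a positive result, without timing relative to dosing.
- Section 6.0, Acute Drug Challenge: the capsule is given on arrival, and neither test is among the Time 0 measures.

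Statements expressly requiring a same-day negative pregnancy test before the first capsule: 0. Statements expressly requiring a same-day negative breath test before it: 0.

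**Exposure that follows.** One capsule at the visit plus 4 × 7 = 28 nightly capsules gives up to 29. This describes what the visit opens the way to. It does not estimate how often a pregnancy would be missed.

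**The case against.** The strongest reply is that the sections, read together, already cover the first-dose visit. Section 5.0 sets a general duty to check continuing eligibility throughout the study, and the two-session sentences only illustrate it. The Acute Drug Challenge is a numbered lab visit, urine is taken on arrival at lab sessions, and Section 13.1 describes one combined pregnancy and toxicology screen. Rescheduling after a positive breath test makes little sense once the study dose has been swallowed, so testing first is the natural reading. Dosing on arrival still allows for intake procedures, since scales and vital signs come first, and Tables 1 and 2 place an alcohol-withdrawal rating at this visit. Contraception is required throughout.

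Most of this stands. It makes some test at or before the first dose likely. It also defeats three stronger conclusions that a reader might draw: that women are dosed untested, that checks happen at only two visits, or that the breath test is read after the capsule. The documents support none of these. BRAINS women have a named test before the first dose, the Section 4.2 rules have no two-session limit, and no sentence places the breath test after dosing. The Section 13.2 heading about tests before scans or assessments concerns confidentiality and settles nothing about order.

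The alcohol side is also weaker than it first looks. Section 7.0 reports no supra-additive effects and no severe or serious events in studies at the highest doses, such as 40 mg of suvorexant. The first dose here is 10 mg under medical supervision, and the trial accepts and discloses that heavy drinkers will then dose at home.

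What the reply does not supply is a sentence that assigns the pregnancy test to this visit or puts either result before the capsule. Staff could follow the text exactly and still give the first dose, and then the four-week supply, without a same-day negative result.

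**Conclusion.** The concern holds in a limited form. The two-session wording in Sections 5.0 and 13.1 does not fit a design with three or five lab visits. The pregnancy test is not expressly assigned to the Acute Drug Challenge, BEHAVIOR women have none tied to any named visit, and neither test is expressly sequenced before the first capsule.

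The residual risk is modest and mainly concerns pregnancy. It cannot be put into numbers, because the documents give neither the proportion of women nor the actual testing practice. Sample size, power and analysis are unaffected. The conclusion rests on the available text: the study-flow figure is not shown and the consent pages were removed, and either might state the order. Tables 1 and 2 schedule interviews and questionnaires, so the absence of urine and breath tests there proves little. This is a cheap improvement to participant safety.

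**What to change.** In Sections 5.0 and 13.1, replace the two-session wording for the pregnancy, toxicology and breath checks with *each lab visit*. In Section 6.0, under the Acute Drug Challenge and Administration Timing, add that a negative urine pregnancy test (women, on the urine already collected for the drug screen) and a negative breath test are recorded at the CRC before the first capsule. Positive results are then handled under the existing termination criteria in Section 5.0: possible termination for pregnancy, rescheduling for alcohol.

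The cost is protocol wording, one test strip per woman at the dosing visit (and at any other visit where one is not already used), and a few minutes before dosing. If the study-flow figure or consent form already states this order, only the wording needs to be aligned.
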